[name], PhD

[name], PhD

[name], PhD

[name], PhD

[name], PhD

[name], PhD

[name], PhD

[name], PhD

[name], PhD

[name], PhD

2. A brief overview of the FINISH trial

Patient/Population	Intervention (standard care)	Comparator (new treatment)	Outcome (primary)
Patients with symptomatic CSDHs requiring surgical burr-hole intervention	Burr-hole surgery with standard intraoperative subdural irrigation	Burr-hole surgery with no intraoperative subdural irrigation	Symptomatic CSDH requiring reoperation within 6 months

2.1 Background and Objectives

Chronic subdural hematoma (CSDH) is the most common type of intracranial hemorrhage and one of the most common diagnoses necessitating neurosurgical care. The incidence of CSDH is sharply rising due to diagnostic improvements and the aging population. The standard care for CSDHs in most countries is a surgical procedure called burr-hole evacuation (craniostomy), followed by intraoperative irrigation and placement of a subdural drain. However, there is a possibility that intraoperative irrigation may not be required, as it potentially leads to increased risks of infections, rebleeding, and patient distress during the procedure performed under local anesthesia. There is also evidence to suggest that irrigation *per se* may be harmful.

We conducted a pragmatic randomized, parallel-group, non-inferiority trial comparing burr-hole craniostomy with intraoperative irrigation and 48h of subdural drainage to the same treatment but with no intraoperative irrigation, with a primary objective to assess the therapeutic value of intraoperative irrigation. We chose the rates of reoperation in the two groups, as an indicator for recurrence of symptomatic CSDH within 6 months.

2.2 Design, Monitoring and Timetable

In this national five-center, stratified, block-randomized (block sizes 4, 6, 8) trial we randomized 587 patients to undergo burr-hole craniostomy of a CSDH in a 1:1 ratio. We compared the effect of burr-hole craniostomy with intraoperative irrigation followed by 48h (± 12 h) subdural drainage (irrigation group) and burr-hole craniostomy without intraoperative irrigation followed by 48h (± 12 h) subdural drainage (no irrigation group) on symptomatic CSDH recurrence requiring reoperation over the course of 6 month follow-up.

The full study protocol of the FINISH study has been published [1]. The trial was designed and conducted by the FINISH investigators and the analyses were completed at the coordinating center. The trial protocol was approved by ethical review at the institutional review board of the Helsinki and Uusimaa Hospital District on November 13, 2019 (HUS/3035/2019) and duly registered at ClinicalTrials.gov (<https://clinicaltrials.gov/ct2/show/NCT04203550>). All participants provided written informed consent. The trial was monitored by Clinical Research Unit of the Helsinki University Hospital (HYKS Institute), Helsinki, Finland. The writing committee of the FINISH trial vouch for the accuracy and completeness of the data, the fidelity of the trial to the protocol, and the complete reporting of adverse events. There was no industry involvement in the trial.

The FINISH trial was launched in the coordinating center (Helsinki) on January 1st, 2020. Due to the Covid-19 pandemic, the next centers joined with some delay, as follows: Oulu University Hospital in July 2020; Kuopio University Hospital in August 2020; Tampere University Hospital and Turku University Hospital in October 2020. All study centers retained in the trial until patient recruitment was completed on August 17, 2022.

2.3 Participants

During the recruitment period of the trial, we screened all patients with a symptomatic CSDH (CT or MRI verified) undergoing burr-hole evacuation in one of the study centers for trial eligibility.

The inclusion criteria were:

- Patients with a symptomatic unilateral or bilateral CSDH requiring burr-hole evacuation
 - o Patients with bilaterally operated CSDHs will be treated with the same protocol on both sides and analyzed as a single study participant
- Predominantly hypodense or isodense on CT imaging (or chronic hematoma on MRI)
- Clinical symptoms correlating with the CSDH
- Patients older than 18 years of age

The exclusion criteria were:

- CSDH requiring surgical treatment other than burr-hole evacuation (eg, craniotomy)

- CSDH in a patient with a cerebrospinal fluid shunt
- Patients who had undergone any prior intracranial surgery
- Comatose patients (Glasgow Coma Scale (GCS) score ≤ 8) with absent motor responses to painful stimuli; decerebrate or decorticate posturing), where rapid hematoma evacuation was required
- postoperative cooperation was suspected to be insufficient for drain usage (ie, disoriented or semiconscious patient)
- had received active treatment for a haematogenic malignancy within the previous 5 years
- Patients with a central nervous system malignancy or tumor that may cause the patient's current symptoms or may interfere with the operation (eg, a small incidental meningioma without associated brain edema, not in the vicinity of the planned burr hole, was not an exclusion criterion)
- acute infection that required antibiotic treatment
- high risk of life-threatening thrombosis (eg, recent coronary stent, intracranial stent, recent pulmonary embolism, low-pressure cardiac valve replacement [mitral or tricuspid valve replacement]) and discontinuation of antithrombotic medication was not recommended

Screening logs were kept at all five centers until the end of the study (August 17, 2022). After being fully informed of the trial protocol, 588 eligible patients willing to participate (written informed consent from patient or next-of-kin) were randomized.

2.4 Randomization and Blinding

After informed consent, a member of the trial group carried out the randomization using an online eCRF system (Granitics Oy, Espoo, Finland). Due to the nature of the treatment, it was not possible to blind the surgeon and the OR staff from the treatment allocation. Measures to minimize bias included:

- The randomization was timed as closely as possible to the time of surgery (just prior to skin incision).
- Neither the patient nor the next-of-kin was informed of the treatment allocation.
- Treatment allocation was not documented in medical records (ie, all personnel participating in patient care after the operation were blinded to allocation).
- The study group members collecting postoperative data, outcome data, imaging data and performing the statistical analyses were blinded to treatment allocation over the entire course of the trial.
- The primary and secondary outcome measures were all evaluated in blinded matter, that is, the outcome assessors were blinded to treatment allocation.
- The study group committed to adhere to the blinded data interpretation analysis plan

2.5 Study Interventions

2.5.1 General surgical technique of the burr-hole surgery

The burr-hole craniostomy was done similarly in all centers, preferably under local anesthesia, with intravenous sedation with benzodiazepines and/ or opioids during the operation. General anesthesia was only used if the neurosurgeon or the anesthesiologist considered it unsafe to perform the procedure under local anesthesia. Routine preoperative antibiotic was given according to local protocols (normally a second-generation cephalosporin 30–60 min prior to incision). The surgeon drilled one 14 mm burr hole over the maximum convexity of the CSDH. In case of bilateral CSDHs, the surgeon performed the same procedure on both sides. If irrigation is used, after opening the dura, the surgeon irrigated the subdural collection with warm (body temperature) Ringer's lactate saline until rinsing appeared clear or at least 200mL (in case of bilateral CSHD, 200 mL per side, i.e., 400 mL total). After that, the surgeon inserted a subdural drain 3–5 cm deep and parallel to skull. The position of the drain (anterior, posterior) was left to the discretion of the surgeon. Burr hole covers or hemostatic were not routinely used (e.g., Spongostan, Tachosil). The type of subdural drain was not standardized, but all study centers used 10F drains applicable for subdural use. Following drain insertion, the proximal end was tunneled approximately 4–5cm from the incision and connected to a passive ventricular drainage bag (through a non-return valve) and the skin incision was closed in two layers (normally absorbable 3–0 suture for subcutis/galea and non-absorbable 4–0 suture for skin). The drain was fixed to the skin in a secure way. The drain-to-skin fixation technique was left to the discretion of the surgeon. The drainage bag was positioned at bed level. The duration of subdural drainage was 48 hours (± 12 hours) [2,3]. Patient mobilization was allowed during drainage (drain is kept open). Prophylactic antibiotics during drainage are not routinely used.

2.5.2 Irrigation group

The burr-hole craniostomy was performed as described earlier. The dura was sharply opened, and 10 mL of subdural exudate was aspirated with a blunt aspiration needle for storage at -75°C to be used for later analysis. The subdural space was irrigated by repeated rinsing with body temperature saline solution with a syringe and blunt

needle until the surgeon considered the exudate to be clear. The minimum irrigation volume was 200 mL per operated side. The subdural drain was inserted 3–5 cm subdurally. Thereafter, the operation was completed as described earlier.

2.5.3. No irrigation group

A burr-hole craniostomy was performed as described earlier. A small incision in the dura was made and 10mL of subdural exudate was aspirated with a blunt aspiration needle for storage at -75°C to be used for later analysis. Directly thereafter, the subdural drain was inserted approximately 3–5 cm subdurally. Thereafter, the operation was completed as described earlier.

2.6 Primary (efficacy) outcome measure

The primary outcome measure was the rate of reoperations of ipsilateral CSDHs within 6 months.

During the execution of the trial, the decision to reoperate was left at the discretion of the neurosurgeon on-call but enforced to adhere to the standard indications of CSDH, thus being identical to indications used for the primary operation (i.e., symptom recurrence or insufficient resolution of clinical symptoms correlating to imaging findings [CT or MR imaging]). All reoperations were conducted according to the current standard of care (burr-hole with irrigation and subdural drain placement). Knowledge of the group-assignment (whether or not irrigation was carried out in the primary CSDH surgery) was not considered necessary and accordingly, unblinding was not carried out prior to or after reoperation.

2.7 Secondary outcome measures

Originally, the FINISH trial was not powered for secondary outcome measure comparisons and these outcomes were considered exploratory (apart from the exception outlined regarding mortality and mRS in the Blinded Data Interpretation). The secondary outcomes included:

- Modified Rankin Scale at 6 months after the operation
- Mortality within 6 months of operation (all-cause mortality)
- Duration of the operation
- Hospital length of stay (index hospital and need for further care)
- CSDH volume reduction at 2 months after the operation
- Adverse events (minor adverse event [MAE], severe adverse event [SAE], procedure-related adverse event [PRAE])

The modified Rankin Scale (mRS) is a validated instrument used to evaluate the level of disability or dependence in individuals with neurological impairments in their activities of daily living [4]. The score ranges from 0 to 6:

- 0 No symptoms
- 1 No significant disability despite symptoms; able to carry out all usual duties and activities
- 2 Slight disability; unable to carry out previous activities, but able to look after own affairs without assistance
- 3 Moderate disability; requiring some help, but able to walk without assistance
- 4 Moderately severe disability; unable to walk without assistance and unable to attend to own bodily needs without assistance
- 5 Severe disability; bedridden, incontinent and requiring constant nursing care and attention
- 6 Dead

2.8 Definition of adverse events

Safety endpoints within 6 months of operation, including the number and severity of adverse events (AE) and procedure-related adverse events (PRAE). Adverse events are categorized as serious adverse events (SAE) and minor adverse events (MAE). We decided to report procedure-related (severe and minor) adverse events separately.

SAE was defined as any inappropriate medical occurrence or effect that results in death, is life-threatening, requires hospitalization or prolongation of an existing inpatient hospitalization, results in persistent or significant disability or incapacity, or is another important medical event.

- Life-threatening in the definition of SAE refers to an event when the patient was at risk of death at the time of the event and does not refer to an event where the event might have hypothetically caused death. Prolonged hospitalization due to delayed transfer will not be considered an AE or SAE.

- Examples of SAEs are death, acute myocardial infarction, pulmonary embolism, systemic infection, acute cerebral infarction (PRAE), intracranial infection (PRAE), epileptic seizures (PRAE) and acute postoperative intracranial hematoma (PRAE).

MAE was defined as clinically mild manifestations, such as the patient possibly being aware of the event or symptom but the event or symptom is easily tolerated by the patient.

- Examples of MAEs are local wound infections manageable with oral antibiotics (PRAE), abnormal skin bleeding from the wound (PRAE), other local infections manageable with oral antibiotics and deep venous thrombosis not causing pulmonary embolism.

2.9 Sample size

2.9.1 Original sample size calculation

The original sample size calculation was presented in the protocol as follows [1]:

The trial is designed to ascertain whether drain without irrigation is non-inferior to drain with irrigation, with the rate of reoperations of ipsilateral CSDHs within 6 months as the primary outcome. We based the standard rate of reoperations (9.6%) on the results from a recent Cochrane review that reported the recurrence rates after CSDH evacuation followed by subdural drainage in six randomized controlled trials (RCTs) with more than 30 patients per treatment arm [5]. This yielded a maximum allowed margin of 9.0% to achieve non-inferiority. Following a consensus meeting with the trial investigators, the non-inferiority margin was lowered to 7.5%. Thus, with a non-inferiority margin of 7.5%, a 2.5% level of statistical significance (alpha=0.025) and an 80% power (beta=0.20), we will need 243 patients per study group [6]. Accounting for a drop-out rate of 10%, the required group size increases to 270 per study group. Accordingly, we set the recruitment target at 540 patients.

5. Deciding on the next meeting and recruitment termination

The next meeting will be held in the mid/end of August 2022. By then we will assess the current sample size and possible recruitment termination whether full sample size has been reached. As of 05/04/2022, the number of patients recruited (intention-to-treat group) is 503/578 (87%).

4. Closing the meeting

The meeting was closed at 13.30 UTC.

3.0 Summary of changes to the original protocol

Original	Final

The study was not powered for secondary outcome measure comparisons and these outcomes were considered exploratory. The secondary outcomes included:
 
 - Modified Rankin Scale at 6 months after the operation - Mortality within 6 months of operation (all-cause mortality) - Duration of the operation - Hospital length of stay (index hospital and need for further care) - CSDH volume reduction at 2 months after operation 	
The study was not powered for secondary outcome measure comparisons and these outcomes were considered exploratory apart from the exception outlined above regarding mortality and mRS in the Blinded Data Interpretation. The secondary outcomes included:
 
 - Modified Rankin Scale at 6 months after the operation - Mortality within 6 months of operation (all-cause mortality) - Duration of the operation - Hospital length of stay (index hospital and need for further care) - CSDH volume reduction at 2 months after operation - Adverse events (minor adverse event [MAE], severe adverse event [SAE], procedure-related adverse event [PRAE])

Accounting for a drop-out rate of 10%, required group size increases to 270 per study group. Accordingly, we set the recruitment target at 540 patients.
	
A non-adherence rate of 15.7% was higher than the originally assumed 10%.
 
The recalculated sample size is 578 patients (289 patients per group). This is calculated as follows:
 $\frac{486}{1 - 0.157} = 576.51.. = 578$

3. Statistical analysis plan (SAP)

3.1 Original statistical analysis plan

The original plan for the statistical analyses was presented in the trial protocol as follows [1]:

The statistical analysis will be performed both according to intention-to-treat (ITT) and PP principles. We will claim non-inferiority of single burr-hole evacuation without irrigation and subdural drainage only if this outcome is supported both by the ITT and the PP analysis. The ITT analysis will be performed using the full analysis set (FAS), defined as all randomized patients in the groups allocated to by the randomization. No exclusions other than caused by missing information will be made. No imputation will take place. The PP analysis will be performed on the subset of the FAS that is compliant with the protocol, have a completed treatment, available measurements and no major protocol violations nor entry criteria violations.

Summary statistics will be presented for both groups. Continuous variables will be presented in terms of mean values or medians with SDs and IQRs, respectively. Categorical variables will be presented with relative frequencies in percent.

The results from the statistical analysis will be considered to support a claim of non-inferiority if the upper limit of a one-sided 97.5% CI (or equivalently a 95% two-sided CI) excludes a difference in the primary endpoint in favor of the IR of more than 7.5%. The center stratification of the randomization will be accounted for in the calculation of the CI.

Exploratory analyses of secondary and other binary endpoints will be performed using the χ^2 test or logistic regression analysis. Continuous outcomes will be analyzed using Student's t-test or analysis of covariance. Potential effect modifiers (patient age, unilateral vs bilateral CSDH, use of antithrombotic medication, preoperative mRS and preoperative clinical status, hematoma density, hematoma size and presence of membranes on preoperative imaging) will be analyzed by including interaction terms in statistical models.

The primary endpoint will be investigated as described above using a CI, which is equivalent to using a non-inferiority test with a one-sided p-value of 0.025 (or a two-sided of 0.05). The statistical testing of other endpoints will also be performed using a two-sided significance level of 0.05. The statistical analysis will be performed using appropriate statistical software packages.

Prior to the statistical analysis, a statistical analysis plan will be finalized and an independent statistician will approve a dataset with sufficient data quality for the statistical analysis. Another statistician blinded to treatment arm will perform the analyses.

3.2 Final statistical analysis plan

The primary outcome for efficacy is the rate of symptomatic CSDH ipsilateral recurrences requiring reoperation within 6 months. The statistical analysis for efficacy will be performed according to both the ITT and PP principles. The ITT analysis will be performed using the full analysis set, defined as all randomized patients in the groups allocated by randomization. No exclusions other than those caused by missing information will be made. No imputation will take place. The PP analysis will be performed on the subset of the full analysis set that is compliant with the protocol, has completed treatment, has available measurements, and has no major protocol violations or entry criteria violations.

As the goal of CSDH surgery is not only to prevent reoperations but also to improve neurological function and prevent death, the entire therapeutic effect (value) of intraoperative irrigation (versus no irrigation) may not be sufficiently comprehensively captured by analysing the primary outcome (rate of reoperations) only. For example, any possible between-group differences in the incidences of deaths and unfavorable functional outcomes may have an effect on the likelihood of a patient being considered for reoperation (i.e., skew the primary analysis).

Prompted by this realization, we deemed it necessary to somehow take into account between-group differences in either mortality and/or unfavorable functional outcome (mRS 0–3 vs. 4–6) in interpreting the findings of the FINISH trial. The approach, to be used in the blinded data interpretation (BDI) [8] of the FINISH trial, is outlined below. In addition, in the event that we will observe a statistically significant difference in the number of deaths

between the two groups, we will carry out a detailed analysis of the causes of death by examining the official death certificates of the participants.

We will claim treatment non-inferiority only if:

- 1) Our primary efficacy analysis, based on the primary outcome, shows non-inferiority and the finding is supported both by the ITT and the PP analyses,
and
- 2) there are no relevant between-group differences in mortality (alive or dead at 6 months) or unfavorable functional outcome (mRS 0–3 vs. 4–6 at 6 months) between the groups (according to an approach outlined in the BDI).

Summary statistics will be presented for both groups. Continuous variables will be presented in terms of mean values or medians with SDs and IQRs, respectively. Categorical variables will be presented with relative frequencies in percent.

The results from the statistical analysis will be considered to support a claim of non-inferiority if the upper limit of a one-sided 97.5% CI (or equivalently a 95% two-sided CI) excludes a difference in the primary endpoint in favor of the irrigation group of more than 7.5%. The center stratification of the randomization will be accounted for in the calculation of the CI.

Exploratory analyses of secondary and other binary endpoints will be performed using the χ^2 test or logistic regression analysis. Continuous outcomes will be analyzed using regression Student's t-test, analysis of covariance or regression models.

Potential effect modifiers will be analyzed by including interaction terms in statistical models for the following subgroups:

- patient age (<70 years, \geq 70 years)
- GCS score at baseline (9–12, 13–14, 15)
- history of head trauma (<4 weeks, \geq 4 weeks, head trauma with unknown timing, no head trauma)
- unilateral versus bilateral CSDH
- use of anticoagulation and/or antiplatelet medication versus none
- preoperative mRS (0–3, 4–5)
- hematoma density (isodense, mixed-density, hypodense)
- hematoma size (width in mm)
- presence of membranes on preoperative imaging (yes, no)

The primary endpoint will be investigated as described above using a CI, which is equivalent to using a non-inferiority test with a one-sided p-value of 0.025 (or a two-sided of 0.05). The between-group comparison of 6-month mortality and mRS 4–6 differences will be compared using 85% and 95% CIs (as outlined in more detail in the BDI). The statistical testing of other endpoints will also be performed using a two-sided significance level of 0.05.

STATA (Statistics/Data analysis, SE v15.1, StataCorp LLC, [name]) will be used for analyses.

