Given that the objective of surgery for CSDH extends beyond preventing reoperations to also encompass the improvement of neurological function and prevention of death, the entire treatment effect of intraoperative irrigation (versus no irrigation) may not be adequately captured by focusing solely on the primary outcome measure, the rate of reoperations. We deemed it crucial to also consider the potential impact of between-group differences in deaths and/or unfavorable functional outcomes, as both could have an effect on the rate of reoperations. We felt that in the name of transparency and trustworthiness, we would need to define *a priori* thresholds for between-group differences in mortality and rate of unfavorable functional outcome (mRS 4–6) at 6-months that we consider “concerning” or “alarming”.

We considered a difference to be “concerning” if the 85% confidence interval (CI) of the absolute between-group difference in mortality or rates of unfavorable functional outcome (mRS 4–6) did not encompass the value of 0.0 and “alarming” if the 95% CI of the absolute between-group difference in mortality or mRS 4–6 rates did not encompass the value of 0.0.

Prior to establishing the thresholds for the 85% CI (“concerning”) and 95% CI (“alarming”) thresholds, we conducted simulations to ensure that these thresholds would yield clinically relevant differences in mortality and unfavorable functional outcome (mRS 4–6) (Figure 4). For the mortality simulations, we assumed a mortality rate of 5% in the standard care group. This selection was based on two recent similar-sized RCTs, in similar settings (Sweden [11], UK [12]), where the 6-month mortality rate was 5% in the groups treated with burr-hole craniostomy and subdural drainage. As for the mRS 4–6 simulations, we assumed an mRS 4–6 rate of 10% based on the results of the DEX-CSDH [12] and DESCA trials [13].

[figure not shown]

Figure 4. Simulation of the 95% (left panel) and 85% (right panel) confidence intervals for between-group differences in 6-month mortality rates (upper panel) and rates of mRS 4–6 (lower panel). The difference in mortality and/or rates of mRS 4–6 is significant if the 85% CI or 95% CI does not encompass the value of 0.0.

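### The 0–3 v 4–6 cut is a fair safety gate, but it is the only mRS comparison specified and it supports a conclusion about functional outcome in general

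*SAP*

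**What the plan says.** Section 2.7 lists "Modified Rankin Scale at 6 months after the operation" as a secondary outcome with no cut, and says of the scale: "The score ranges from 0 to 6". Section 3.2 explains why reoperation alone is not enough: "the goal of CSDH surgery is not only to prevent reoperations but also to improve neurological function and prevent death". The findings are therefore to be read in the light of group differences "in either mortality and/or unfavorable functional outcome (mRS 0–3 vs. 4–6"). It then makes the non-inferiority claim conditional on there being no relevant difference in mortality or "unfavorable functional outcome (mRS 0–3 vs. 4–6 at 6 months) between the groups".

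On method, section 3.2 states: "The between-group comparison of 6-month mortality and mRS 4–6 differences will be compared using 85% and 95% CIs". For the rest it says: "Exploratory analyses of secondary and other binary endpoints will be performed using the χ^2 test or logistic regression analysis". Continuous outcomes get a t-test, analysis of covariance or regression models. No ordinal or shift analysis is named.

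Section 4 (blinded data interpretation), Step 3, gives the planning rate: "we assumed an mRS 4–6 rate of 10" per cent. It also assumes 5% mortality. Table 4 defines two thresholds for a relevant difference in mRS 4–6: concerning if the 85% CI excludes zero, and alarming if the 95% CI does. If no imbalance is found, Step 3 adds a ready-made sentence to the conclusion that the groups did not differ relevantly in mortality or functional outcome. Step 5 repeats that sentence for every primary-outcome result.

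**The concern.** The reason given for using the mRS (function improves or does not) is wider than the comparison chosen (severely disabled or dead, or not). By the level definitions in section 2.7, a patient with no symptoms and one who needs some help but walks unaided both count as favourable. At the planning rate about nine patients in ten fall in that group.

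The cost falls on the wording of the conclusion. A worse distribution without irrigation within mRS 0–3 would leave the gate untouched, and the report would still say that functional outcome showed no relevant difference. The data that could show such a shift are collected in any case. The listed secondary outcome, the uncut mRS, has no defined analysis.

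**Working it through.** **1. The plan's own sample size.** Inputs from section 2.9: reoperation rate 9.6%, margin 7.5%, one-sided alpha 0.025, power 80%.
n per arm = (1.960 + 0.842)² × 2 × 0.096 × 0.904 / 0.075² = 242.2, so 243. Then 486/0.90 = 540, and 486/(1 − 0.157) = 576.5, which the plan sets at 578, or 289 per arm. This reproduces. The SAP gives no power figure for the mRS.

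**2. What the cut can detect.** Inputs: 10% in one arm (Step 3), 289 per arm, Wald CI of the difference.
- An assumed common odds ratio of 1.5 gives p₂ = 1.5 × 0.10 / (0.90 + 1.5 × 0.10) = 14.3%.
- SE = √(0.10 × 0.90/289 + 0.143 × 0.857/289) = 0.0271, so z = 0.0429/0.0271 = 1.58.
- Power at the 95% CI: Φ(1.58 − 1.96) = 35%. At the 85% CI: Φ(1.58 − 1.44) = 56%.
- For 80% power the other arm would need about 18.0% (95% CI) or 16.4% (85% CI).

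**3. What an ordinal comparison can detect.** Under proportional odds, information on the log odds ratio is N(1 − Σp̄³)/12, with N = 578 and p̄ the level probabilities averaged over the arms. Power = Φ(ln 1.5 × √information − z). The SAP gives no distribution within 0–3, so five spreads were assumed, all with 3%, 2% and 5% at levels 4, 5 and 6.

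| Assumed % at mRS 0/1/2/3 | Power, 95% | Power, 85% | Cut's share of ordinal information |
|---|---|---|---|
| 22.5 at each level | 79% | 91% | 28% |
| 25/25/20/20 | 79% | 91% | 28% |
| 10/15/25/40 | 76% | 89% | 29% |
| 60/15/10/5 | 73% | 87% | 35% |
| 75/8/4/3 | 62% | 79% | 47% |

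For the first row, Σp̄³ = 0.044, information = 578 × 0.956/12 = 46.1, and 0.405 × √46.1 = 2.75. For the last row, Σp̄³ = 0.357, information = 578 × 0.643/12 = 31.0, and 0.405 × √31.0 = 2.26. The last column is (0.10 × 0.90/4) / ((1 − Σp³)/12) on the control distribution, that is 0.0225 divided by 0.0795 down to 0.0481.

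Simulation with 20,000 trials per case and a tie-corrected rank-sum test agrees within about one percentage point. At an odds ratio of 1.3 and the 95% level, the cut has 17% and the ordinal comparison 30–43%. At 1.7 the figures are 56% and 85–95%.

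**4. Two cases that break the common odds ratio** (starting from 25/25/20/20).
- *Shift wholly within 0–3*, to 15/20/25/30: the true difference on the cut is zero, so it flags only at its nominal error rate (about 5% or 15%). A rank test at the 5% level detects it in about 92% of trials.
- *Harm only at the 3/4 boundary*, seven percentage points moving from level 3 to level 4 (10% v 17%): the cut has about 70% power at the 95% CI. The rank test has about 6%.

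**The case against.** The strongest defence is that the cut serves another purpose. Section 3.2 also argues that deaths and poor outcomes affect who is considered for reoperation and so could distort the primary comparison. Step 3 is headed as a safety analysis, its thresholds were set in advance after simulation, and the SAP says openly that the trial is not powered for them. A safety gate may reasonably use a severe cut. This stands, and it is why the cut should stay. It does not justify a closing sentence about functional outcome in general.

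It can also be said that section 3.2 does not forbid other mRS analyses, since it allows regression models and promises relative frequencies for categorical variables. That is right as far as it goes: the method for the uncut scale is undefined, not excluded. But regression models are attached to continuous outcomes, and none is named for the mRS.

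Three stronger readings are tempting, and the documents do not support them:
- *The cut misses most of the functional change.* The SAP gives no distribution within 0–3, and patients at preoperative mRS 4–5 who reach 0–3 are counted.
- *The cut largely repeats mortality.* On the planning figures 5%/10%, half of the 4–6 events are deaths. The other half are survivors with severe disability.
- *An ordinal analysis should replace the cut.* The 3/4 boundary case in the working shows the cut performing far better there. A common odds ratio favours the ordinal method by construction.

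The 35% figure should not be quoted alone either, because Table 4 also treats the 85% CI as a threshold for a relevant difference.

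**Conclusion.** The point holds as a mismatch between what is compared and what is concluded. The safety gate itself is not at fault.

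Under a common odds ratio of 1.5 and 10% in mRS 4–6, the cut raises no mRS flag in about 44% of trials at the 85% CI and about 65% at the 95% CI. An ordinal comparison would miss about 9–21% and 21–38% at the matching levels. The size depends on the assumed spreads and on proportional odds. The direction is the same across all five spreads, and reverses when harm is confined to the 3/4 boundary. That the cut cannot register a difference lying wholly within 0–3 needs no assumption.

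This is a cheap improvement to a secondary analysis and to one sentence of the conclusion. It does not invalidate the non-inferiority rule.

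**What to change.** 1. Leave the 0–3 v 4–6 comparison and its 85% and 95% thresholds unchanged.
2. In section 3.2, specify a supportive proportional-odds analysis of the 6-month mRS, with death as level 6, adjusted for preoperative mRS and centre. Report the common odds ratio with its 95% CI.
3. Show that odds ratio and the seven-level distribution for Groups A and B alongside Tables 5 and 6.
4. In Steps 3 and 5, narrow the no-imbalance sentence to *no relevant differences in mortality or in the rate of mRS 4–6*.
5. Fix the rule before unblinding: if the 95% CI of the common odds ratio excludes 1, the shift is reported in the discussion as exploratory. Without such a rule, the extra result would bring back the discretion that the blinded interpretation was written to remove.

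The cost is one extra model on data already collected. It brings in the proportional-odds assumption, which can be checked against the seven-level table. It is also insensitive to a difference confined to the 3/4 boundary, which the retained cut covers.
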